## 4.3. Screen Failures and Rescreening

Screen failures are defined as subjects who consent to participate in the clinical study but are not subsequently enrolled in the study because they do not meet eligibility requirements. A minimal set of screen failure information will be collected that includes demography, screen failure details, eligibility criteria, medical history, prior therapies, and any serious adverse events.

Individuals who do not meet the criteria for participation in this study (screen failure) may be rescreened only once.

## 4.4. Subject Number and Identification

Subjects will have a unique identification number used at Screening. Subjects will be assigned a subject number prior to the first dosing occasion. Assignment of subject numbers will be in ascending order and no numbers will be omitted (e.g., Subjects 0101, 0102, 0103). Replacement subjects will be assigned a subject number corresponding to the number of the subject he/she is replacing plus 1000 (e.g., Subject 1101 replaces Subject 0101).

Subjects will be identified by subject number only on all study documentation. A list identifying the subjects by subject number will be kept in the Site Master File.

## 4.5. Subject Withdrawal and Replacement

A subject is free to withdraw from the study at any time. In addition, a subject will be withdrawn from dosing if any of the following criteria are met:

- change in compliance with any inclusion/exclusion criterion that is clinically relevant and affects subject safety as determined by the Investigator (or designee)
- noncompliance with the study restrictions that might affect subject safety or study assessments/objectives, as considered applicable by the Investigator (or designee)
- occurrence of any Common Terminology Criteria for Adverse Events (CTCAE) v5 Grade ≥3 AE

- occurrence of Grade 2 AE considered by the Investigator (or designee) to be at least possibly related to sotorasib and, in the opinion of the Investigator (or designee), warrants subject withdrawal (e.g., neuropathy, chronic diarrhea, etc.)
- any clinically relevant sign or symptom that, in the opinion of the Investigator (or designee), warrants subject withdrawal.

If two or more subjects are withdrawn from the study due to AEs that are considered by the Investigator to be at least possibly related to sotorasib or if there is one Grade 3 event, dosing would be paused, and the Investigator and Sponsor will convene to review the data and determine the next step.

If a subject is withdrawn from dosing, the Sponsor (or designee) will be notified and the date and reason(s) for the withdrawal will be documented in the subject's electronic Case Report Form (eCRF). If a subject is withdrawn, efforts will be made to perform all EOS assessments, if possible (Appendix 9). Other procedures may be performed at the Investigator's (or designee's) and/or Sponsor's discretion. If the subject is inhouse-, these procedures should be performed before the subject is discharged from the clinic. The Investigator (or designee) may also request that the subject return for an additional follow-up visit. All withdrawn subjects will be followed until resolution of all their adverse events and serious adverse events, or until the unresolved adverse events and serious adverse events are judged by the Investigator (or designee) to have stabilized.

Subjects who are withdrawn for reasons not related to study drug may be replaced following discussion between the Investigator and the Sponsor. Subjects withdrawn as a result of adverse events/serious adverse events thought to be related to the study drug will generally not be replaced.

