# 4.7. Discontinuation of Study Treatment

Subjects (or a legally acceptable representative) can decline to continue receiving investigational product and/or other protocol-required therapies or study procedures at any time during the study

but continue participation in the study. If this occurs, the Investigator is to discuss with the subject the appropriate processes for discontinuation from investigational product or other protocol-required therapies and must discuss with the subject the possibilities for continuation of the Schedule of Assessments (Appendix 9) including different options of follow-up (e.g., in person, by phone/mail, through family/friends, in correspondence/communication with other treating physicians, from the review of medical records) and collection of data, including endpoints, adverse events, serious adverse events and must document this decision in the subject's medical records. Subjects who have discontinued investigational product and/or other protocol-required therapies or study procedures should not be automatically removed from the study. Whenever safe and feasible, it is imperative that subjects remain on study to ensure safety surveillance and/or collection of outcome data.

Reasons for removal from protocol-required investigational product(s) or procedural assessments include any of the following:

- Decision by the Sponsor
- Lost to Follow-up
- Death
- Protocol deviation
- Noncompliance
- Adverse events
- Subject request
- Pregnancy.

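### The first limb of the dosing-pause rule counts subjects withdrawn from the study, but Section 4.5 withdraws them from dosing, so two related withdrawals below Grade 3 need not trigger it

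*Protocol*

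**What the plan says.** Protocol Section 4.5 first lets a subject leave the study at any time. It then adds a separate action: "a subject will be withdrawn from dosing if any of the following criteria are met". Two of the listed criteria can be met by a related event below Grade 3: a Grade 2 event at least possibly related to sotorasib that the investigator thinks warrants withdrawal, and any clinically relevant sign or symptom that the investigator thinks warrants it.

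The study-level pause rule follows and has two limbs. The first reads "If two or more subjects are withdrawn from the study due to AEs that are considered by the Investigator to be at least possibly related" (meaning related to sotorasib). The second reads "or if there is one Grade 3 event, dosing would be paused". Either limb leads to a pause and a joint data review by investigator and sponsor. The next paragraph goes back to the dosing wording: "If a subject is withdrawn from dosing, the Sponsor (or designee) will be notified".

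Section 4.7 treats coming off product and leaving the study as different things. It says that subjects who have discontinued product "should not be automatically removed from the study", and then "Whenever safe and feasible, it is imperative that subjects remain on study". Adverse events appear in the list that it introduces with "Reasons for removal from protocol-required investigational product(s) or procedural assessments include any of the following".

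**The concern.** The individual stopping action and the event that the pause rule counts are described in different words, and Section 4.7 gives the difference practical content. A site that stops a subject for a related Grade 2 event and keeps the subject under observation has followed both sections, yet on the literal wording that subject does not count toward the first limb.

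The first limb is the only mandatory pause that covers repeated related events below Grade 3. According to the Amendment 2 summary, the pausing criteria were added on the recommendation of the regulatory agency, so the trigger should work as intended without interpretation. The study is multi-center, and sites could read the wording differently. The same two adverse events could then lead to a pause or not, depending on whether the subjects were kept on study.

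**Working it through.** The plan gives no figure to reproduce here. Alpha, power, variability and sample size play no part. The check applies the rule as written to one scenario: two subjects are stopped from dosing for possibly related adverse events below Grade 3, and no Grade 3 event has occurred.

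**Inputs**

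- Action on each subject: withdrawal from dosing (Section 4.5).
- First limb: at least 2 subjects withdrawn from the study for possibly related adverse events (Section 4.5).
- Second limb: 1 Grade 3 event (Section 4.5).
- Status after stopping product: not automatically off study, and to stay on study where safe and feasible (Section 4.7).

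**Count under the first limb.** Let k be the number of the two subjects who stay on study. The literal count is 2 − k. If withdrawals from dosing also counted, the count would be 2 whatever the value of k.

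| Subjects kept on study (k) | Literal count, 2 − k | Threshold of 2 met? | Count if withdrawal from dosing also counts | Threshold of 2 met? |
|---|---|---|---|---|
| 0 | 2 | yes | 2 | yes |
| 1 | 1 | no | 2 | yes |
| 2 | 0 | no | 2 | yes |

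**Count under the second limb.** There is no Grade 3 event in the scenario, so the count is 0 against a threshold of 1.

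**Other rules that might force a pause.** Appendix 7 sets hepatotoxicity stopping rules for individual subjects, not a study-level pause. Section 4.6 lets the sponsor stop the study for safety or any other reason, but does not oblige a review after a given number of withdrawals. Sponsor notification under Section 4.5 carries no count and no pause.

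**Result.** If both subjects stay on study, as Section 4.7 asks, the first limb stands at 0 of 2, the second at 0 of 1, and no mandatory pause applies.

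**The case against.** The best answer is that Section 4.5 uses withdrawal as a single status. After the opening list it speaks of withdrawn subjects without qualification. It sends them to the end-of-study assessments, which the Appendix 9 footnote assigns to the end of study or to a subject who leaves the study early. Its closing paragraph, on subjects withdrawn for drug-related events, draws no line between dosing and study. The Amendment 2 rationale describes the added criteria as criteria for withdrawal from the study. Section 4.7 opens with subjects who decline further product, so it can be read as aimed mainly at them. The practical loss is also small: the investigator makes the withdrawal decision and the sponsor is told of it, so both would already know of both cases.

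Much of this stands. It makes it probable that the terms were meant as one, and the notification duty is a real safeguard. But no operative sentence says that withdrawal from dosing counts toward the pause. The sentences in Section 4.7 about staying on study are not limited to subjects who decline product, and the list there names adverse events. Knowing of two cases is also not the same as being required to pause and review them.

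A reader might go further and infer that the protocol leaves repeated lower-grade events unwatched, or that a probability of a missed pause can be calculated. The documents support neither. Notification, the Grade 3 limb and the sponsor's power to stop the study all remain. A probability would need the share of stopped subjects who stay on study, whether that decision is independent between subjects (a site may well apply one policy to all) and the rate of such withdrawals. None of these is given. Section 3.3 says only that 960 mg was well tolerated in 6 healthy-subject studies with 2 to 3 administrations, so such cases may be few.

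**Conclusion.** The rule is wrong as written, and the point is minor. On the literal text, two related withdrawals from dosing below Grade 3 with both subjects kept on study give a count of 0 where 2 is required, and no other mandatory pause takes over. The conclusion rests on reading *withdrawn from the study* in its ordinary sense and on Section 4.7 applying to subjects stopped for adverse events.

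Its practical size is unknown. If 0% of such subjects stay on study, as the end-of-study route in Section 4.5 suggests, the wording has no effect. If 100% stay, the first limb is never met by withdrawals from dosing. The evidence points to loose wording, not to a decision to leave these subjects out. No endpoint, analysis or sample size is affected.

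**What to change.** In the first limb of the pause rule in Protocol Section 4.5, insert the three words *dosing or from* after *withdrawn from*, so that it counts subjects withdrawn from dosing or from the study for adverse events at least possibly related to sotorasib. Leave the count of two, the grade thresholds and the Grade 3 limb as they are.

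The cost is one sentence in a protocol amendment, with the usual ethics and regulatory handling, and no extra visits, samples or subjects. The downside is that a pause review may be convened somewhat more often.

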# 4.6. Study Termination

The Sponsor may stop the study or study site participation in the study for medical, safety, regulatory, administrative, or other reasons consistent with applicable laws, regulations, and Good Clinical Practice. Both the Sponsor and the Investigator reserve the right to terminate the Investigator's participation in the study according to the Clinical Trial Agreement. The Investigator is to notify the Institutional Review Board (IRB) in writing of the study's completion or early termination and send a copy of the notification to the Sponsor. The Sponsor reserves the unilateral right, at its sole discretion, to determine whether to supply investigational product and by what mechanism, after termination of the study.

In addition, the study may be terminated by the Sponsor at any time and for any reason. If the Sponsor decides to terminate the study, they will inform the Investigator as soon as possible.

# 4.7. Discontinuation of Study Treatment

Subjects (or a legally acceptable representative) can decline to continue receiving investigational product and/or other protocol-required therapies or study procedures at any time during the study

but continue participation in the study. If this occurs, the Investigator is to discuss with the subject the appropriate processes for discontinuation from investigational product or other protocol-required therapies and must discuss with the subject the possibilities for continuation of the Schedule of Assessments (Appendix 9) including different options of follow-up (e.g., in person, by phone/mail, through family/friends, in correspondence/communication with other treating physicians, from the review of medical records) and collection of data, including endpoints, adverse events, serious adverse events and must document this decision in the subject's medical records. Subjects who have discontinued investigational product and/or other protocol-required therapies or study procedures should not be automatically removed from the study. Whenever safe and feasible, it is imperative that subjects remain on study to ensure safety surveillance and/or collection of outcome data.

Reasons for removal from protocol-required investigational product(s) or procedural assessments include any of the following:

- Decision by the Sponsor
- Lost to Follow-up
- Death
- Protocol deviation
- Noncompliance
- Adverse events
- Subject request
- Pregnancy.

# 5. STUDY TREATMENTS

Study treatment is defined as any investigational product, non-investigational product, placebo, or medical device intended to be administered to a study subject according to the study protocol.

Note that in several countries, investigational product and non-investigational product are referred to as investigational medicinal product and non-investigational medicinal product, respectively.

# 5.1. Investigational Product

The IMP will be supplied by the Sponsor. The Investigational Product Instruction Manual, a document external to this protocol, contains detailed information regarding the storage, preparation, destruction, and administration of the IMP shown in Table 2.

All supplies of investigational product, both bulk and subject-specific, will be stored in accordance with the manufacturer's instructions or pharmacy instructions. Until dispensed to the

subjects, the investigational products will be stored at the study site in a location that is locked with restricted access.

# 5.2. Investigational Product Administration

# Table 2:Investigational Product

	(Treatment A, C) Investigational Medicinal Product:	(Treatment B) Investigational Medicinal Product:
Study Treatment Name	Sotorasib	Sotorasib
Unit Strength and Formulation	320 mg tablet	120 mg tablet
Dosage Level	960 mg (3 x 320 mg tablets)	960 mg (8 x 120 mg tablets)
Route of Administration	Oral	Oral
Accountability	The quantity administered, date administered, and lot number of investigational product are to be recorded on each subject's Case Report Form.	The quantity administered, date administered, and lot number of investigational product are to be recorded on each subject's Case Report Form.

Dosing Instructions	Treatment A: The	The Investigator/designee will
	Investigator/designee will	administer the treatment after the
	administer the treatment after the	completion of all predose procedures
	completion of all predose	and after a fast of at least 10 hours.
	procedures and after a fast of at	Eight tablets should be taken (the first
	least 10 hours. Three tablets should	tablet by itself immediately followed
	be taken (the first tablet by itself	by seven tablets) with 8 ounces (240
	immediately followed by two	mL) of water. Additional water may
	tablets) with 8 ounces (240 mL) of	be used during dosing, as required.
	water. Additional water may be	Tablets should not be broken or
	used during dosing, as required.	chewed.
	Tablets should not be broken or chewed.	No food will be given for at least
	No food will be given for at least	4 nours post administration.
	4 hours post administration.	
	Treatment C: The	
	Investigator/designee will	
	administer the treatment after the	
	completion of all predose	
	procedures and after a fast of at	
	least 10 hours. Subjects will	
	consume the entirety of a standard	
	high-fat breakfast within 20	
	minutes. A 960-mg dose of	
	sotorasib will be given orally 30	
	minutes after start of the meal.	
	first tablet by itself immediately	
	followed by two tablets) with	
	8 ounces (240 mL) of water	
	Additional water may be used	
	during dosing, as required. Tablets	
	should not be broken or chewed.	
	No food will be given for at least	
	4 hours post administration.	

Except as part of the dose administration, subjects will restrict their consumption of water for 1 hour prior to dosing and for 2 hours after dosing; at all other times during the study, subjects may consume water as desired. Subjects will continue fasting for at least 4 hours postdose.

Subjects will be dosed while standing and will not be permitted to lie supine for 2 hours after administration of IMP, except as necessitated by the occurrence of an adverse event(s) and/or study procedures.

# 5.2.1. Standard High-fat Meal

The standardized high-fat meal breakfast should consist of approximately 800 to 1000 calories (including approximately 150 protein calories, 250 carbohydrate calories, and 500 to 600 fat calories). A typical meal is equivalent to 2 eggs fried in butter, 2 strips of bacon, 2 slices of

buttered toast or bread, 4 ounces of hash brown potatoes (fried with butter), and 8 ounces (240 mL) of whole milk. Substitutions can be made as long as the meal provides a similar amount of calories from protein, carbohydrate, and fat and has similar meal volume and consistency. Substitutions will apply to all subjects and all subjects will receive an identical meal.

## 5.3. Treatment of Overdose

The effects of overdose of sotorasib are not known. In case of overdose, consultation with the medical monitor is recommended for prompt reporting of clinically apparent or laboratory adverse events possible related to over dosage, and to discuss further management of the subject.

## 5.4. Medical Devices

Other non-investigational medical devices may be used in the conduct of this study as part of standard care. Non-Amgen non-investigational medical devices (e.g., syringes, sterile needles), that are commercially available are not usually provided or reimbursed by the Sponsor (except, for example, if required by local regulation). The Investigator will be responsible for obtaining supplies of these devices.

## 5.5. Product Complaints

A product complaint is any written, electronic, or oral communication that alleges deficiencies related to the identity, quality, durability, reliability, safety, effectiveness, or performance of a drug(s) or device(s) after it is released for distribution to market or clinic by either the Sponsor or by distributors and partners for whom the Sponsor manufactures the material. This includes any investigational product (sotorasib) provisioned and/or repackaged/modified by the Sponsor.

Any product complaint(s) associated with an investigational product (sotorasib) supplied by the Sponsor are to be reported according to the instructions provided in the Amgen IPIM.

## 5.6. Randomization

In Period 1 and Period 2, subjects will be randomized 1:1 into 1 of 2 treatment groups based on the study randomization scheme that will be provided by a biostatistician. Subjects in Period 3 will not be randomized.

## 5.7. Blinding

This is an open-label study.

# 5.8. Treatment Compliance

The following measures will be employed to ensure treatment compliance:

• All doses will be administered under the supervision of suitably qualified study site staff.

- Immediately after dose administration, visual inspection of the mouth and hands will be performed for each subject.
- At each dosing occasion, a predose and postdose inventory of IMP will be performed.

# 5.9. Drug Accountability

The Investigator (or designee) will maintain an accurate record of the receipt of sotorasib tablets received. In addition, an accurate drug disposition record will be kept, specifying the amount dispensed to each subject and the date of dispensing. This drug accountability record will be available for inspection at any time. At the completion of the study, the original drug accountability record will be available for review by the Sponsor upon request.

For each batch of unit doses, the empty used unit dose containers will be discarded upon satisfactory completion of the compliance and accountability procedures. Any unused assembled unit doses will be retained until completion of the study.

# 6. CONCOMITANT THERAPIES AND OTHER RESTRICTIONS

## 6.1. Concomitant Therapies

Subjects will refrain from use of any prescription or nonprescription medications/products during the study until the EOS, unless the Investigator (or designee) and/or Sponsor have given their prior consent.

Acetaminophen (paracetamol; up to 2 g/day) is an acceptable concomitant medication. The administration of any other concomitant medications during the study is prohibited without prior approval of the Investigator (or designee), unless its use is deemed necessary for treatment of an adverse event/serious adverse event. Any medication taken by a subject during the course of the study and the reason for its use will be documented in the source data.

## 6.2. Diet

Subjects will be fasted overnight (at least 8 hours) before collection of blood samples for clinical laboratory evaluations. While confined at the study site, subjects will receive a standardized diet at scheduled times that do not conflict with other study-related activities.

Refer to Section 5 and Table 2 for diet requirements/restrictions on applicable days of study treatment and/or PK assessments.

Foods and beverages containing poppy seeds, grapefruit, or Seville oranges will not be allowed from 7 days prior to check-in until EOS.

Caffeine-containing foods and beverages will not be allowed from 48 hours before Check-in until EOS.

Consumption of alcohol will not be permitted from 48 hours prior to Check-in until EOS.

#### 6.3. Smoking

Subjects will not be permitted to use tobacco- or nicotine-containing products within 6 months prior to Check-in until the EOS.

